#### 5.9 Procedures for Monitoring Subject Compliance

For the MMF maintenance arm, pill counts of the MMF will be performed at each visit, Week 4 through Week 60, to assess compliance.

For the MMF withdrawal arm, pill counts of the MMF will be performed at each visit, Week 4 through Week 12, to assess compliance.

#### 5.10 Treatment Discontinuation and Subject Withdrawal

#### 5.10.1 Study Treatment Discontinuation

Study drug provided by the sponsor will be discontinued for any individual subject under the following conditions:

- 1. At any time during the study at the request of the subject or subject's guardian.
- 2. If investigators or NIAID determine that the subject's health, safety, and/or wellbeing are threatened.
- 3. For either disease activity or toxicity guidelines as outlined below:
  - Disease Activity: If the subject meets the primary endpoint of clinically significant disease reactivation, the study drug will be discontinued and subject treated at the discretion of the investigator per Section 5.3.1, *Administration of Study Product in Response to SLE Reactivation*, but the subject will continue study visits. Clinically significant disease reactivation is defined in Section 3.2 *Description of Primary Endpoint*.
  - Toxicity or Infection:
    - If the subject must discontinue study drug for more than 14 sequential days due to ongoing, suspected MMF toxicity, then study drug will be discontinued, but the subject will continue study visits.
    - If the subject has study drug withheld for a cumulative total of 28 days or greater in the setting of multiple or recurrent MMF toxicity, study drug will be discontinued, but the subject will continue study visits.
- 4. If the subject is female and becomes pregnant.
- 5. Subject non-compliance with treatment regimens or failure to keep appointments.

Subjects who discontinue protocol-specified treatment requirements will be treated as medically indicated according to discretion of the treating physician.

#### 5.10.1.1 Procedures for Discontinuation of Protocol-Specified Treatment Requirements

Whenever possible, subjects who have been discontinued from study treatment for disease activity or toxicity should complete all remaining scheduled study visits including all exams, procedures, assessments, and tests. Furthermore, if study treatment discontinuation is due to safety concerns, subjects will be given appropriate care under medical supervision beyond the last scheduled study visit, if necessary, per Sections 7.3.4, *Recording Adverse Events*, and 7.3.5, *Recording Serious Adverse Events*. If the site PI determines that completion of these visits is not clinically appropriate for the subject or if the subject or subject's guardian elects not to complete these visits, the subject will be withdrawn from the study per the guidelines in Section 5.10.2, *Subject Withdrawal from the Study*.

#### 5.10.2 Subject Withdrawal from the Study

When a subject is withdrawn from the study, protocol-specified treatment requirements are discontinued, and all study-related visits, exams, procedures, assessments, tests and data collection are terminated. Individual subjects will be withdrawn from the study under the following conditions:

- 1. The subject or subject's guardian withdraws consent.
- 2. The investigator or NIAID believes it is in the best interest of the subject.
- 3. The subject is lost to follow-up.
- 4. The study is terminated.

#### 5.10.2.1 **Procedures for Subject Withdrawal from the Study**

Whenever possible, subjects to be withdrawn from the study will be asked to consent to an end-of-study evaluation, which includes all scheduled exams, procedures, and laboratory tests planned for the Week 60 visit. Furthermore, if discontinuation is due to safety concerns, subjects will be given appropriate care under medical supervision beyond the last scheduled study visit, if necessary, until the symptoms of any AE resolve or the subject's condition becomes stable. After this end-of-study visit, the PI (or designated treating physician) may continue to follow the subject to manage clinical care, but no additional study-related data will be collected.

#### 5.10.3 Safety Stopping Guidance

The DSMB will review any event that potentially impacts safety at the request of the protocol chair or DAIT/NIAID. The DSMB will have discretion to recommend actions regarding study conduct and continuation as a consequence of any planned or unplanned monitoring activity.

The DSMB will be informed in real time of the following event:

• Any immediately life-threatening event or death that occurs in the study, which is possibly, probably, or definitely related to study participation.

In addition, the following events will trigger both a comprehensive DSMB Emergency Safety Review and a temporary halt in enrollment:

- Events that result in permanent discontinuation of study intervention occurring in
  - 3 of the first 10 subjects randomized to the MMF withdrawal or
  - $\circ$  30% of subjects randomized to MMF withdrawal at any time point after the 11th subject is randomized.
- BILAG\* A flares occurring in
  - 3 of the first 10 subjects randomized to MMF withdrawal or
  - $\circ$  30% of subjects randomized to MMF withdrawal at any time point after the  $11^{\text{th}}$  subject is randomized.
- Severe SELENA-SLEDAI\* flares occurring in
  - 3 of the first 10 subjects randomized to MMF withdrawal or
  - $\circ$  30% of subjects randomized to MMF withdrawal at any time point after the  $11^{\text{th}}$  subject is randomized.

In the event of a temporary halt in enrollment, no new subjects will be consented, randomized or start on study product; subjects already on study product will continue unless they are the focus of the DSMB review. Subjects in the screening phase of the study may continue to undergo minimal risk procedures (e.g., blood tests), but more than minimal risk procedures should be deferred. Randomization will not occur until the DSMB review is complete. After careful review of the data, the DSMB will make recommendations regarding study conduct and/or continuation.

In addition, at each planned Data Review Meeting, the DSMB will review the estimated risk difference for disease reactivation (i.e. risk\_MMFwithdrawal - risk\_MMF maintenance) and consider whether or not the trial should be stopped for safety concerns. (See Section 8.4 *Interim Analysis* for details.)

# 6 ASSESSMENT OF SAFETY AND DISEASE ACTIVITY

# 6.1 Assessments of Safety

To assess safety in this population, peripheral blood cell counts, liver function, and serum creatinine will be monitored before enrollment and at frequent intervals thereafter. A physical examination will be conducted at each study visit. The information from these assessments will be used to characterize the frequency of all AEs, all SAEs, as well as the other safety endpoints noted in Section 3.3.2, *Secondary Safety Endpoints*.

# 6.2 Assessments of Disease Activity

Clinically significant disease reactivation (defined in Section 3.2 *Description of Primary Endpoint*) is the primary endpoint of this trial. Disease activity will be monitored by evaluating clinical outcomes at screening and serially throughout the trial.

The m-SLEDAI\* will be assessed at screening and the SELENA-SLEDAI\* along with medications will be assessed at each study visit to evaluate clinically significant disease reactivation. SLE disease activity will also be assessed by administration of the BILAG\* and the SLICC/DI\*. The original lupus instruments include an evaluation of proteinuria based on the protein:creatinine ratio derived from a 24-hour urine. For this study, the protein:creatinine ratio will typically be derived from the spot urine assessment although a 24-hour urine may be used if the spot urine assessment is not available.

Quality of life will be assessed by administration of the FACIT, SF-36®, and Lupus QoL©.

#### 6.3 Mechanistic Studies

Secondary mechanistic objectives overall are to define biomarkers, which are associated with increased risk of disease flare in SLE patients.

#### 6.3.1 Serologic Markers

Serum for serologic markers including C3, C4, and antibodies to dsDNA, Sm, RNP, SSA/Ro and SSB/La will be collected at every scheduled visit and every Flare Visit.

C3, C4, and dsDNA antibodies (anti-dsDNA) are needed at each visit as part of the SELENA-SLEDAI\* scoring system, but will also be analyzed as independent markers to define the utility of the markers in predicting which subjects will meet the primary endpoint of clinical disease activation.

Antibodies to Sm, RNP, SSA/Ro, and SSB/La will be measured from a serum specimen at Baseline and Week 60 for all subjects. To evaluate these markers as predictors of flare, samples collected at pre-flare, flare, and post-flare time points may be analyzed for those subjects who flare. For subjects who do not flare, samples may be analyzed at three additional time points for comparison to the results for flaring subjects.

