# 1.5.1 **Rationale for the Inclusion Criteria**

Inclusion criteria require patients to have been clinically stable/quiescent for a sustained time period, such that by standard care principles they could consider discontinuation of MMF. The longer sustained period of MMF treatment in the setting of renal involvement reflects the randomized clinical data indicating benefit from MMF maintenance therapy for two or more years. Serological activity will not prohibit entry into the trial, as the predictive capacity of serologies for SLE flare are questionable in the setting of prolonged clinical quiescence [29]. Because we do not wish to have serological activity prohibit trial enrollment, a modification of the SLEDAI, the m-SLEDAI, will be used at screening to determine eligibility. The m-SLEDAI is identical to the SLEDAI except for the exclusion of double-stranded DNA antibodies (anti-dsDNA) and hypocomplementemia [1]. An m-SLEDAI score of < 4 at

screening will allow enrollment in the trial. Minor/transient or nonspecific clinical symptoms are allowed at entry (see Appendix A, *Definition of Mild Disease*), as major immunosuppressant therapy would not be warranted for such symptoms. If the subject is on prednisone therapy for SLE, the dose must have been  $\leq 10 \text{ mg/day}$  (or equivalent dose of alternative corticosteroid) for 12 weeks and stable for 4 weeks prior to randomization as a reflection that the subject has been clinically quiescent (see Section 5.5.2, *Prednisone (or Equivalent)* for the definition of "stable dose").

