12	Hematuria	> 5 red blood cells per high power field. Exclude stone, infection, or other causes.		4					
13	
 
> 0.5 protein:creatinine ratio. New onset or recent increase of more than 0.5 on the protein:creatinine ratio.
 
Proteinuria Note: ALE06 will typically use a spot urine protein:creatinine ratio. If only the 24-hour urine is available, then proteinuria is defined as: ">0.5 gm/24 hours. New onset or recent increase of more than 0.5 gm/24 hours."
 
			4					
14	Pyuria	> 5 white blood cells per high power field. Exclude infection.		4					
15	Rash	Ongoing inflammatory lupus rash.		2					
16	Alopecia	Ongoing abnormal, patchy, or diffuse loss of hair due to active lupus.		2					
17	Mucosal ulcers	Ongoing, oral or nasal ulcerations due to active lupus.		2					
18	Pleurisy	Classic and severe pleuritic chest pain, or pleural rub, or effusion, or new pleural thickening due to lupus.		2					
19	Pericarditis	Classic and severe pericardial pain, or rub, or effusion, or electrocardiogram confirmation.		2					
20	Low complement	Decrease in CH50, C3, or C4 below the lower limit of normal for testing laboratory.		2					
21	Increased DNA binding	> 25% binding by Farr assay or above normal range for testing laboratory.		2					
22	Fever	> 38°C. Exclude infectious cause.		1					
23	Thrombo- cytopenia	< 100,000 platelets/mm  [equivalent to 100 x10  /L]		1					
24	< 3,000 white blood cells/mm 			1					

Total Score (sum of weights next to descriptors marked present):

MII	D OR MODERATE FLARE
	Change in SLEDAI > 3 points
	New/Worse
	
 
Discoid, photosensitive, profundus, cutaneous vasculitis, bullous lupus
 
Nasopharyngeal ulcers
 
Pleuritis
 
Pericarditis
 
Arthritis
 
Fever attributable to SLE
 

	Increase in prednisone, but not to $> 0.5 \text{ mg/kg/day}$
	Added NSAID or Plaquenil
	$\geq$ 1.0 increase in Physician's Global Assessment (PhGA), but not to more than 2.5 (on a 3.0 indexed VAS scale—refer to the Physican's Global Assessment located on the Modified SLEDAI Source Document)
SEV	ERE FLARE
	Change in SLEDAI > 12
	New/Worse 
 
CNS-SLE
 
Vasculitis
 

	• Nephritis
	• Myositis $P_{1} = P_{2} = $

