#### SELENA-SLEDAI:

The SELENA-SLEDAI instrument will be completed at baseline and every follow-up visit, including any Flare or Endpoint visits, during the course of the 60 week study period for all subjects. Data for this assessment will be collected on the *Physician's Global Assessment*, *SLEDAI*, and *SELENA Flare & Endpoint Assessment* CRF pages. The SELENA-SLEDAI assesses SLE disease activity and flares based on changes in the SLEDAI score, the Physician's Global Assessment (PGA), medication use (prednisone, NSAIDS, Plaquenil, major immunosuppressives), other disease activity criteria, and hospitalization due to SLE.

Study investigators complete the SLEDAI scale by indicating of presence of 24 SLE disease manifestations during the preceding 10 days. The original SLEDAI instrument includes an evaluation of proteinuria based on the protein:creatinine ratio derived from a 24-hour urine. For this study, the protein:creatinine ratio will typically be derived from the spot urine assessment although a 24-hour urine may be used if the spot urine assessment is not available. Each of the 24 disease manifestations has an assigned weight (see Appendix 14.3). The SLEDAI total score will be computed as the sum of the weights for the items indicated as present. If a component of the SLEDAI (urinalysis or hematological labs only) was missed at a visit, then the missing data will be imputed by using the last observation carried forward approach. If a component of the SLEDAI is missed over consecutive visits, then the subsequent components will not be imputed. If an entire visit was missed, the score will not be imputed.

Mild/moderate and severe SELENA-SLEDAI flares will be defined per the table below. If one or more criteria for a mild/moderate or severe flare have been met, a subject will be considered as having a mild/moderate or severe flare at that study visit.

MILD OR MODERATE FLARE		
	Change in SLEDAI > 3 points	
	New/Worse Discoid, photosensitive, profundus, cutaneous vasculitis, bullous lupus Nasopharyngeal ulcers	Pleuritis Pericarditis Arthritis
		Fever attributable to SLE
	Increase in prednisone, but not to > 0.5 mg/kg/day 	
	Added NSAID or Plaquenil	
	≥ 1.0 increase in Physician's Global Assessment (PhGA), but not to more than 2.5 (on a 3.0 indexed VAS scale—refer to the Physican's Global Assessment located on the Modified SLEDAl Source Document)	
SEVERE FLARE		
	Change in SLEDAI > 12	
	New/Worse CNS-SLE Vasculitis Nephritis Myositis	-0

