# 7.4.2. Changes in C3, C4, and anti-dsDNA Levels

**Endpoint**: C3, C4, and anti-dsDNA are run at baseline and every follow-up visit, including any Flare or Endpoint visits, during the course of the 60 week study period and run by a central laboratory. Change from baseline will be calculated for each test and time point.

Specifically, change from baseline in levels of C3, C4, and anti-dsDNA at Week 20, the time of first flare, and immediately prior to first flare will be analyzed.

Version: 1.0 Page 29 of 48

**Analysis**: Descriptive statistics (mean, standard deviation, median, minimum, maximum and number of subjects in a group) will be computed by treatment group and separately for subjects who do/do not experience clinically significant disease reactivation at each specified time point. Summary statistics will be plotted versus time at the relevant time points. Plots for individual subjects will also be created.

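### C3/C4 and anti-dsDNA can supply up to 4 points of the SLEDAI change (threshold > 3) that defines the first flare at which the SAP describes those same markers

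*Protocol*

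**What the plan says.** - **Double use of the markers.** Protocol 6.3.1 says that C3, C4 and anti-dsDNA are required at every visit to score the SELENA-SLEDAI, "but will also be analyzed as independent markers to define the utility of the markers in predicting which subjects will meet the primary endpoint".
- **Their place in the score.** In Protocol Appendix C and SAP 14.3, item 20 (low complement: "Decrease in CH50, C3, or C4 below the lower limit of normal for testing laboratory") and item 21 (increased DNA binding: "> 25% binding by Farr assay or above normal range for testing laboratory") each have weight 2.
- **The flare rule.** SAP 7.2.1 lists "Change in SLEDAI > 3 points" among the mild/moderate criteria and a change above 12 among the severe ones. Meeting any one criterion is enough. The section does not name the visit from which change is counted.
- **The marker analyses.** SAP 7.4.1 covers levels of the three markers at Baseline, at Week 20, at first flare and just before it. SAP 7.4.2 covers "change from baseline in levels of C3, C4, and anti-dsDNA at Week 20, the time of first flare, and immediately prior to first flare". Both are descriptive, by treatment group and by reactivation status.
- **A serology-free score already exists.** Protocol 1.5.1 says: "The m-SLEDAI is identical to the SLEDAI except for the exclusion of double-stranded DNA antibodies (anti-dsDNA) and hypocomplementemia". It is used for eligibility at screening, not for flare.
- **Planned sensitivity analyses.** SAP 7.2.3 (item 3) sets aside flares due only to a new or increased immunosuppressant, and SAP 7.3.2 and 7.3.3 may do so. None sets aside flares due only to serology.

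**The concern.** A marker that forms part of the definition of an event will look abnormal at that event whatever its biological relation to it. Here the blood results that score items 20 and 21 can define first flare, and the same results are then tabulated at first flare. A reader of those tables could take low complement and raised anti-dsDNA at flare as evidence that serology tracks flare, when part of the pattern follows from the scoring rule.

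This matters because Protocol 2.2.3 lists dsDNA antibodies, C3 and C4 among the markers of particular interest, while Protocol 1.5.1 calls the predictive value of serology questionable in prolonged clinical quiescence. A score containing serology is a poor instrument for settling that doubt.

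**Working it through.** The plan gives no figure to reproduce. The check is on the scoring rule.

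**1. Serology alone.** Both items newly positive, nothing else changed: 2 + 2 = 4. Since 4 > 3, this is a mild/moderate flare. Since 4 is not > 12, it cannot be a severe flare by score.

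**2. Net change.** The criterion is a net change, so a fall elsewhere can cancel the gain. Entry allows an m-SLEDAI below 4. If a rash present at entry (2 points) clears while both serologies convert, the change is 4 − 2 = 2, which is not a flare.

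**3. Serology plus one clinical item.** One newly positive serology item with one new 2-point item (rash, alopecia, mucosal ulcers, pleurisy, pericarditis) also gives 2 + 2 = 4. Several of these have their own new/worse flare criterion (nasopharyngeal ulcers, pleuritis, pericarditis, certain rashes). Serology is therefore decisive mainly for alopecia and for rashes outside that list.

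**4. Room to gain, if change is counted from baseline.**

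| Baseline serology | Largest gain from items 20 and 21 | Crosses > 3 alone |
|---|---|---|
| Neither positive | 4 | yes |
| One positive | 2 | no |
| Both positive | 0 | no |

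Under that assumption, subjects serologically active at entry have fewer routes to a flare, which would push a baseline association the opposite way. SAP 7.2.1 does not settle the reference visit, so this is only a possibility.

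**5. Which tables are touched.**
- At first flare, marker and event can come from the same visit, so the overlap is direct.
- At Week 20, overlap arises for subjects flaring at that visit. SAP 7.4.1 and 7.4.2 do not set them apart.
- Baseline values, and Week 20 values that precede a later flare, are not the same measurement as that flare.

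**6. Primary endpoint.** It needs a flare and a sustained increase in therapy. Comparing the therapy routes with the SAP 7.2.1 flare criteria:
- Routes 2a and 2b.i (steroid increase): an increase in prednisone is itself a flare criterion, so serology is not needed.
- Route 2c with new azathioprine, methotrexate or MMF: itself a severe-flare criterion, so serology is not needed.
- Route 2b.ii (repeated injected or IV steroid), an increased MMF dose, or an agent not listed: no criterion in the SAP 7.2.1 table plainly matches, so serology could decide. SAP 7.2.3 does appear to treat increased immunosuppressants as a possible cause of flare, which would narrow this group further.

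**7. Illustration of size, with assumed inputs.** Suppose serology is unrelated to clinical flare. Let f be the risk of a clinical flare (0.1 to 0.5) and q the chance that both items convert together (0.02 to 0.20), with no offsetting falls. Then P(flare) = 1 − (1 − f)(1 − q), and the share of flare subjects with double conversion is q / P(flare).
- f = 0.5, q = 0.02: P(flare) = 1 − 0.5 × 0.98 = 0.51; share = 0.02 / 0.51 = 3.9%.
- f = 0.1, q = 0.20: P(flare) = 1 − 0.9 × 0.8 = 0.28; share = 0.20 / 0.28 = 71.4%.

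Among subjects without flare the share is 0% by definition. The documents give neither f nor q, so this shows only that a difference arises with no true association.

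**The case against.** The strongest reply has five parts.

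- **The stated outcome is the primary endpoint, not flare.** Protocol 1.5 requires a treatment change as well as a flare in order to raise specificity. This stands: serology alone can never meet the endpoint. A reader might infer that the primary comparison is contaminated. Step 6 does not support that, because most qualifying treatment increases supply the flare themselves.
- **Protocol 2.2.3 asks about baseline and Week 20 markers, not at-flare values.** This largely stands. A reader might infer that the objective cannot be answered, but the at-flare summaries are a separate listed assessment in Protocol 3.3.3. Only Week 20 values in subjects flaring at that visit carry the overlap into the objective.
- **The SAP plans descriptive summaries, and 'independent' may mean only 'separately'.** This is fair, and the Protocol sentence itself discloses that the markers belong to the score. Descriptive tables can still mislead about a built-in difference.
- **The analysis uses levels while the score uses cut-offs.** True, so the overlap is partial.
- **Keeping the full published instrument is legitimate, and a second flare definition gives these markers a different first-flare date from the cytokine and gene-expression assessments.** This is a reason to add a repeat analysis and not to replace the planned one.

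**Conclusion.** The overlap is real and follows from the scoring rule: up to 4 points against a threshold of > 3. It affects the at-flare levels and changes in SAP 7.4.1 and 7.4.2, and Week 20 values in subjects flaring at that visit.

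Two stronger readings should be avoided. Double conversion is not always a flare, because other items can fall. An opposite bias at baseline is not established, because it requires change to be counted from baseline and the SAP does not say so.

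The effect on the primary endpoint is probably small. It cannot be put at zero: SAP section 12 reports 8 reactivations among the first 80 subjects, so one event that relied on these items would be 1/8 = 12.5% of them. The documents do not give the actual number. This is a worthwhile and cheap improvement to secondary analyses, not a flaw in the primary analysis.

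**What to change.** - **SAP 7.4.1 and 7.4.2:** keep the planned summaries and repeat them with first flare and reactivation derived from SLEDAI-change criteria computed without items 20 and 21.
- **SAP 7.3.2:** add a sensitivity analysis in which a flare met only through items 20 and 21 does not count. This parallels the medication-only analysis already described there.
- **Reporting:** state how many first flares and how many primary endpoints depended on those two items. For the primary endpoint the count is enough, since a full sensitivity analysis would probably change few subjects.
- **Protocol 6.3.1:** replace 'independent' with 'separate'.

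The cost is one extra derived variable from SLEDAI item data already on the CRF, and slightly fewer flares in the repeated tables. The primary analysis and trial conduct do not change. The medication and physician-global routes to flare remain, so treatment or a global score prompted by serology would still count. The overlap is reduced, not eliminated.
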